Study Protocol

Official Title: Using Data-Driven Implementation Strategies to Improve the Quality of Cirrhosis Care

ClinicalTrials.gov ID (NCT number): NCT04178096

Protocol Date: September 9, 2021

Scientific Background

Cirrhosis, or advanced liver disease, affects approximately four million people in the US. Approximately 100,000 Veterans under the care of the Veterans Health Administration (VA) have cirrhosis due to alcohol, hepatitis C (HCV), fatty liver disease, or other causes, and this number is rapidly increasing. There are lifesaving measures that providers can take to prevent harm from cirrhosis, including providing access to screening for liver cancer. However, less than 30% of Veterans receive guideline-concordant cirrhosis care.

In 2015, the VA's HIV, Hepatitis and Related Conditions Program Office (HHRC) established the national Hepatic Innovation Team (HIT) Learning Collaborative as part of its efforts to improve Veterans' access to new, highly effective HCV treatments. The PI's previous work evaluating the HIT Collaborative program identified specific implementation strategies that were associated with higher rates of HCV treatment using an annual 73-item survey based on the Expert Recommendations for Implementing Change (ERIC) implementation strategy taxonomy.

In 2018, the HIT Collaborative's focus pivoted from HCV elimination towards cirrhosis care. The PI's evaluation team and other investigators aimed to develop a manualized cirrhosis care intervention that would help VA facilities develop and roll-out implementation strategies unique to their needs. The framework for this manualized intervention was based on an implementation strategy bundle called Getting To Outcomes (GTO), a 10-step approach that guides organizations through the process of choosing, implementing, evaluating, and improving an evidence-based practice (EBP) or intervention. While GTO had been applied to many content domains and settings, it had yet to be tested in healthcare settings. In addition, GTO was designed for selection of effective *interventions*, not for the selection of *implementation strategies* to implement a pre-specified intervention.

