The GTI manual will guide the intervention. It includes step-by-step instructions through the GTI steps, worksheets, and resources. The GTI manual specifies eight “core” strategies found to be empirically associated with better cirrhosis care outcomes. Each of the core implementation strategies includes an accompanying appendix to aid in operationalizing it, and a tracking form to document use and fidelity.

Meetings

GTI facilitators will hold biweekly, 1-hour virtual meetings for a 6-month period to guide the participating facility's implementation team through GTI. This will be followed by 3 additional meetings over the 6-month sustainment period.

Toolkit

The GTI Toolkit includes editable versions of worksheets from the GTI manual. Participating facilities will complete these tools collaboratively with facilitators during meetings.

Data Collection

Facilitators will track GTI implementation and fidelity from several sources. A tracking spreadsheet will be used to record the time spent on each step, how and by whom GTI tools were completed, challenges encountered, and other relevant field notes. Additional sources include contemporaneous notes from biweekly meetings; completed GTI tools; and summative interviews with local implementation teams asking about their experiences with GTI and facilitation, the core strategies, and barriers and facilitators experienced.

Clinical outcomes at the facility- and patient-level will be obtained from the national Advanced Liver Disease Dashboard, which uses data from the VA's Corporate Data Warehouse (CDW) to identify Veterans with cirrhosis and to track interventions such as abdominal imaging (i.e., liver cancer screening).

Study Population

VA Facilities

We will enroll up to 12 VA facilities in the lowest quartile of guideline-concordant cirrhosis care. Implementation will be conducted in three steps over a 2-year period, with four facilities crossing from control to intervention every 6 months until all sites are exposed to the intervention.

Veterans

Veterans with cirrhosis engaged in care at a participating VA facility will be included in analysis. Engagement in care will be defined as having at least one encounter for clinical care in the prior 18 months. Veterans will be assigned to the facility in which they receive their primary care at the time of randomization.

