Study Statistical Analysis Plan (SAP)

Official Title: Using Data-Driven Implementation Strategies to Improve the Quality of Cirrhosis Care

ClinicalTrials.gov ID (NCT number): NCT04178096

Document Date: December 30, 2024

Statistical Analysis Plan

Data were analyzed using intent-to-treat principles, such that Veterans were assigned to their Veterans Health Administration (VA) facilities at the start of the study and all VA facilities were included in analysis (other than those no longer part of the VA Corporate Data Warehouse due to change to the Cerner electronic health record mid-trial). The primary question was whether GTI was associated with improved hepatocellular carcinoma (HCC) surveillance rates at the end of intervention and at 12 months post intervention. This was assessed using generalized linear mixed models with logistic regression. Investigators first modeled the association between Getting to Implementation (GTI) and HCC surveillance without adjustment for individual- or facility/cluster-level covariates. Subsequently, they adjusted for individual- and cluster-level covariates, and then did sensitivity analyses to assess whether removing early pandemic period (January 1, 2020–September 30, 2020) data impacted models. These models all assessed the patient-level binary outcome of receipt of HCC surveillance in the 6-month period. Initially, investigators specified three random effects: the random effect for the repeated measures from individual i in cluster k , the random cluster-by-time interaction, and the within-cluster ICC. However, the cluster-by-time interaction was found to be unneeded because it approximated 0. Note that the assignment of interventions is confounded with time in the stepped-wedge, cluster-randomized trials, so modeling the background secular trend is important to remove the bias in estimating the effect attributed solely to the intervention. Investigators assume that the average secular trend is a distinct value during each period, and they used a nonparametric representation for the time effect (categorical time).

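### Does cutting January to September 2020 out of models of a six-month outcome make the pandemic sensitivity analysis unsound?

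*SAP*

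**What the plan says.** The SAP (section Statistical Analysis Plan) fits an unadjusted model and then an adjusted one. It then asks whether "removing early pandemic period (January 1, 2020–September 30, 2020) data impacted models". The next sentence defines the outcome for the whole set: "These models all assessed the patient-level binary outcome of receipt of HCC surveillance in the 6-month period".

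On time, "Investigators assume that the average secular trend is a distinct value during each period", and time enters as a categorical factor. A random cluster-by-time term was specified at first, but "the cluster-by-time interaction was found to be unneeded because it approximated 0".

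The Protocol (Study Population, VA Facilities) plans up to 12 facilities in three steps, "with four facilities crossing from control to intervention every 6 months until all sites are exposed to the intervention".

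Neither document gives the calendar limits of the analysis periods, the first date of the data, the crossover dates, or a rule for a period that lies partly inside the removed window. The SAP is written in the past tense and describes analyses already done.

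**The concern.** There are two reasons for suspicion.

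First, nine months is one and a half six-month periods. If the cut was made by calendar date, some period would keep only part of its months, and surveillance in that remnant would be scored as though six months had been available. Rates in that period would be too low, and the model would mix outcome windows of different length.

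Second, a separate mean for each period already removes a pandemic drop that every facility shared. The GTI effect is at risk from a drop that differed between facilities, and the cluster-by-time term that might have captured it is no longer in the model. If removing the window tested only for the shared drop, agreement between the two analyses would be false reassurance about the main threat to a stepped-wedge trial run through 2020.

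**Working it through.** The documents give no figure on this point to reproduce. From the documents: the window dates, the 6-month outcome, categorical time, 6-month steps, and three steps of four facilities. Assumed for illustration: surveillance rates of 20% to 45% (the Protocol's Scientific Background says only that "less than 30% of Veterans receive guideline-concordant cirrhosis care"), two or three all-control periods, and a shock of 1 logit confined to the first two of them.

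**1. Calendar.** 1 January to 30 September 2020 is 274 days, or 9 months; 9/6 = 1.5 periods. Laid over each possible grid of six-month periods:

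| Periods start in | Months removed from each touched period | Months left |
|---|---|---|
| Jan/Jul | 6, 3 | 0, 3 |
| Feb/Aug | 1, 6, 2 | 5, 0, 4 |
| Mar/Sep | 2, 6, 1 | 4, 0, 5 |
| Apr/Oct | 3, 6 | 3, 0 |
| May/Nov | 4, 5 | 2, 1 |
| Jun/Dec | 5, 4 | 1, 2 |

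Every grid has one or two partly covered periods. Dropping touched periods whole would cost 2 × 6 = 12 or 3 × 6 = 18 months. There is an exception: on an April/October grid with data starting on 1 January 2020, the first period was already only January to March, and the window creates no new remnant.

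**2. If a three-month remnant were kept.** With a constant imaging rate, q = 1 − √(1 − p).

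| Six-month p | Three-month q | Shift in log odds |
|---|---|---|
| 20% | 10.6% | −2.14 − (−1.39) = −0.75 |
| 30% | 16.3% | −1.63 − (−0.85) = −0.79 (unrounded) |
| 40% | 22.5% | −1.23 − (−0.41) = −0.83 (unrounded) |
| 45% | 25.8% | −1.05 − (−0.20) = −0.85 |

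The fall in level is large but nearly the same at every rate, so one period effect takes up most of it. What is left in the treatment contrast is small:

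- 20% versus 30%: odds ratio 1.71 becomes 1.65.
- 30% versus 40%: 1.56 becomes 1.49.
- 30% versus 45%: 1.91 becomes 1.79.

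These changes apply within the remnant period only. The pooled estimate also draws on the full periods.

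**3. Which pandemic shock moves the estimate?** Take six periods and three sequences crossing at the start of periods 3, 4 and 5, with facility and period effects. Let x be the treatment indicator and r its residual after removing facility and period means.

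- Facility means of x are 4/6, 3/6 and 2/6; the grand mean is 1/2; the period mean is 0 in periods 1 and 2.
- So in each of periods 1 and 2, r = 0 − 4/6 − 0 + 1/2 = −1/6 for the first sequence, 0 for the second and +1/6 for the third.
- The sum of r·x is 1/3 in each sequence, 1 in total. This is the denominator; four facilities per sequence scale numerator and denominator alike.
- Shared shock of −1: bias = 2 × (−1) × (−1/6 + 0 + 1/6) / 1 = 0.
- Shock of −1, −0.5, 0 by sequence: bias = 2 × [(−1/6)(−1) + 0 × (−0.5) + (1/6)(0)] / 1 = +0.33 logit; reversed, −0.33.
- With periods 1 and 2 removed, the shock is no longer in the data and the bias is 0 in every case.

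With facility random intercepts instead (between-facility to residual variance ratio 0.5 to 10, two or three all-control periods), the differential shock gives a bias of 0.20 to 0.33 in absolute value, and 0 after removal. A logistic model with facility and period effects, fitted to expected proportions with true log odds ratio 0.40, gives:

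| Shock | All data | Window removed |
|---|---|---|
| Shared | 0.400 | 0.400 |
| Differs by sequence | 0.669 | 0.400 |
| Differs, reversed | 0.132 | 0.400 |

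The standard error rises by 3% (0.474 to 0.489) to 9% (0.499 to 0.544). The shared shock is therefore the case in which removal changes nothing in expectation. A difference between sequences is what makes the two analyses disagree.

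**The case for a change.** The best case for action is that the analysis cannot be reproduced from the SAP. The mismatch between 9 and 6 months is a matter of arithmetic, the text is complete at that point, and it contains no handling rule. If a period was shortened, its outcome is not the stated one; if it was dropped whole, the stated dates understate what was removed. One sentence would settle it.

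The factual part of this stands. So do two limits of the check. It reaches only effects inside the window, so uneven recovery after 30 September 2020 is untouched. And with at most 12 facilities, a cluster-by-time variance near zero does not exclude a shock that followed randomization sequence.

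The rest does not carry. That remnants were kept is an inference, and the sentence on the six-month outcome, covering all the models, points away from it. Dropping or redefining the overlapping periods is what an analyst holding to that outcome would do. Adding a facility-specific random effect for the early-pandemic periods would gain little: it is a restricted form of the term already fitted and found near zero, and it is not aimed at a shock that follows sequence. Removing the window addresses that case directly.

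**Conclusion.** The concern does not call for a change. Its calendar arithmetic is right, but truncated outcomes are not documented. Had a three-month remnant been kept on a calendar common to all facilities, the illustrated odds ratios within that one period would fall by 0.06 to 0.12 (1.71 to 1.65, 1.91 to 1.79), in a sensitivity analysis only. The claim that the check sees only a shared shock is the wrong way round: a shared shock gives zero bias with or without the window, while a shock of up to 1 logit that differed by sequence biases the full-data estimate by 0.20 to 0.33 logit on the linear scale, and removal takes that bias away. The SAP asks only whether removal affected the models; it does not present the result as proof that the pandemic had no influence.

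The sizes rest on assumed rates, a constant imaging rate, and a shock confined to early all-control periods. The last cannot be confirmed without the crossover dates. That a shared shock is absorbed and a sequence-dependent one is not follows from the categorical time effect itself. What is left is a gap in reporting that analysts fill sensibly, in a secondary check.

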Thus, "Getting to Implementation" (GTI) was created to support the selection, tailoring, and use of implementation strategies in health care settings. An adaptation of GTO, GTI was developed using the evaluation team's surveys to identify effective strategies associated with improved cirrhosis care, as well as interviews with providers at VA facilities that were performing well on guideline-concordant cirrhosis care metrics.

This study aims to test the effectiveness of GTI to increase cirrhosis EBP uptake in VA facilities that are performing low on cirrhosis care metrics.

Study Objectives

The goal of this study is to assess the effectiveness of GTI's set of prescribed data-driven implementation strategies in increasing liver cancer screening for Veterans with cirrhosis at participating VA facilities. GTI is an 8-step program supported by a facilitation team with clinical and evaluation expertise that provides participating facilities' implementation teams with guidance and training to select and implement effective strategies to best fit their needs in order to improve care.

Study Design & Methods

This interventional study is a hybrid type III, stepped-wedge, cluster-randomized trial. Participating facilities will be randomized to the time that they receive the intervention. All intervention activities will be completed virtually.

Study Procedures

Intervention

Getting to Implementation (GTI) is an 8-step intervention involving biweekly meetings with a 2-person facilitation team. In addition to the participating facility's preliminary step of forming a local implementation team, GTI steps include:

- Step 1 – Identify Gaps and Goals
- Step 2 – Assess Facilitators and Barriers
- Step 3 – Choose Implementation Strategies
- Step 4 – Adapt Strategies and Address Readiness
- Step 5 – Plan Implementation
- Step 6 – Implement and Evaluate
- Step 7 – Improve Implementation
- Step 8 – Sustain Implementation

The intervention is delivered to the participating facility's implementation team over a 6-month active implementation period, followed by a 6-month sustainment period.

Manual

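### GTI is tailored by each facility, but the SAP's final model assumes one GTI effect everywhere; if effects vary, the interval for the average effect is too narrow and its p-value too small.

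*SAP*

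**What the plan says.** The SAP's primary analysis is a logistic mixed model with categorical time. On the random part it states: "Initially, investigators specified three random effects: the random effect for the repeated measures from individual i in cluster k", followed by a random cluster-by-time term and a within-cluster term. It then reports that "the cluster-by-time interaction was found to be unneeded because it approximated 0". The final model therefore has individual and facility intercepts only. The SAP describes no facility-level random GTI effect, no robust variance and no small-sample correction. The one sensitivity analysis it names removes early-pandemic data.

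The protocol (Scientific Background) says GTI "was created to support the selection, tailoring, and use of implementation strategies in health care settings". Under Study Objectives, facility teams receive "guidance and training to select and implement effective strategies to best fit their needs in order to improve care". Under Study Procedures each site forms its own team, chooses strategies (Step 3) and adapts them (Step 4), and facilitators record "how and by whom GTI tools were completed, challenges encountered, and other relevant field notes". There is also a common core: "The GTI manual specifies eight “core” strategies found to be empirically associated with better cirrhosis care outcomes", with one manual, the same eight steps and biweekly facilitation at every site.

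On size, Study Population says: "We will enroll up to 12 VA facilities in the lowest quartile of guideline-concordant cirrhosis care", "with four facilities crossing from control to intervention every 6 months until all sites are exposed to the intervention". The SAP excludes facilities that left the Corporate Data Warehouse when they changed to Cerner.

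**The concern.** An intervention whose content is chosen and adapted locally may work better at some sites than at others. A model with one common effect measures the precision of that effect from Veterans and periods, as if every facility estimated the same quantity. If facilities truly respond differently, the average response is known only as well as at most 12 facility-specific responses allow, however many Veterans each one contributes.

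At stake is the primary conclusion. A few responsive facilities could produce an average odds ratio whose interval excludes 1 when an interval that allowed for the variation would not. The dropped cluster-by-time term does not settle this. It represents independent shocks in each facility-period, whereas a facility-specific GTI effect is absent before crossover and then persists.

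**Working it through.** The documents give no power calculation, ICC, facility size or between-facility SD for this model, so there is no stated figure to reproduce.

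**Inputs from the documents.** 12 facilities, 3 waves of 4 and six-month periods (protocol, Study Population); categorical time (SAP). A 30% rate is a proxy: Scientific Background says fewer than 30% of Veterans receive guideline-concordant cirrhosis care, which is not the HCC surveillance rate itself.

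**Assumptions.** 4 to 6 periods; m = 500 Veterans per facility (200 and 1000 as checks); facility-intercept SD 0.4; within-person correlation ρ = 0.3; SD of the GTI log-odds effect between facilities, τ, from 0 to 0.3; two-sided Normal test at 0.05.

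**Step 1: model covariance.** Work with facility-period logits. The sampling variance is v = 1/(m × p × (1 − p)) = 1/(500 × 0.3 × 0.7) = 0.0095. For each facility, W = 0.4² J + v[(1 − ρ)I + ρJ], where J is the all-ones matrix and I the identity. This stands for the SAP's facility and individual intercepts.

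**Step 2: true covariance.** V = W + τ² x x′, where x is the facility's 0/1 GTI exposure over periods.

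**Step 3: compare.** Let X hold the period indicators and x. The model variance is A⁻¹ with A = Σ X′W⁻¹X. The true variance of the same estimator is A⁻¹ (Σ X′W⁻¹VW⁻¹X) A⁻¹. The ratio r is true SE over model SE, and the actual error rate is 2[1 − Φ(1.96/r)].

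Example, 4 periods, τ = 0.15: r = 0.0624/0.0446 = 1.40, and 2[1 − Φ(1.96/1.40)] = 0.16.

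| τ | True SE / model SE (4 to 6 periods) | Error when the average effect is zero |
|---|---|---|
| 0 | 1.00 | 0.05 |
| 0.1 | 1.20–1.26 | 0.10–0.12 |
| 0.15 | 1.40–1.52 | 0.16–0.20 |
| 0.2 | 1.65–1.82 | 0.23–0.28 |
| 0.3 | 2.20–2.49 | 0.37–0.43 |

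Facility size matters: at τ = 0.2 the error runs from 0.13 (200 Veterans, 4 periods) to 0.41 (1000 Veterans, 6 periods). With ρ = 0 the ratios fall; at 500 Veterans and 4 periods they are 1.14 at τ = 0.1 and 1.48 at τ = 0.2.

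To picture τ: with no average effect, τ = 0.1 puts 95% of facility odds ratios between exp(−0.196) = 0.82 and exp(0.196) = 1.22.

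**Step 4: what the near-zero cluster-by-time term rules out.** A varying GTI effect leaks partly into that term. The implied cluster-by-time variance is about 0.0024–0.0027 at τ = 0.1, 0.010–0.011 at 0.2 and 0.022–0.025 at 0.3. The SAP gives neither the estimate nor a threshold, so two readings were simulated (4 periods; 200 / 500 Veterans).

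- Strict, estimated SD below 0.05 (250 trials per cell, no separate individual effect): met in 57% / 50% of trials at τ = 0.1, 14% / 6% at 0.2 and 4% / 0.4% at 0.3. Repeating this with ρ = 0.3 gave 54% / 55%, 15% / 3% and 0.7% / 0%.
- Loose, estimated variance below 0.01 (120 trials per cell, ρ = 0.3): met in 83% / 89% at τ = 0.15 and 47% / 52% at τ = 0.2.

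So the SAP's remark fits τ of about 0 to 0.15. It fits 0.2 only on the loose reading, and 0.3 is very unlikely.

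**The case against.** A reader might infer that the reported interval is too narrow as a matter of fact. The documents do not support that. They report no between-facility SD, and at SD 0 the ratio is exactly 1.00. Different content does not entail different effects: the manual, the eight core strategies with their tracking forms, and the facilitation are common, and tailoring to local barriers could even out effects. This stands, and the point is therefore conditional.

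A reader might also take the largest error rates at face value. The SAP did fit a cluster-by-time term, and its near-zero value is real, though partial, evidence against large variation. That also stands. It does not close the question, because the term has the wrong shape for a persistent effect and its estimate is not reported.

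The error rates should not be read as false positives when GTI does nothing anywhere. In that case the SD is 0 and omitting the random effect does no harm. They apply when effects vary around a zero average.

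Finally, the target is ambiguous. Study Objectives speaks of the facilities taking part, while the end of Scientific Background speaks of low-performing VA facilities. For an average over only the participating sites, between-site variation is not necessarily sampling error. This narrows the point for a reader who wants that average. It does not help one who wants to generalise beyond these sites.

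**Conclusion.** The concern holds conditionally. The final model assumes one GTI log-odds effect at every facility, the design gives reason to doubt that, and the SAP describes no check or protection. If effects vary, the interval for the average effect across such facilities is too narrow and its p-value too small.

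The range best supported by the SAP's own remark is an SD of about 0 to 0.15. At 500 Veterans per facility that means a standard error understated by a factor of 1.0 to about 1.5, and an error rate of 0.05 to 0.20 for a zero average effect. These figures rest on assumed facility size, intercept SD, within-person correlation and number of periods, and on a reading of near zero that the SAP does not define.

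**What to change.** Keep the stated model. Report the GTI odds ratio with a facility-clustered variance that carries a small-sample correction. Add a sensitivity model with a facility-level random GTI effect, and report the average odds ratio with its interval from that model and the estimated between-facility SD. Give the cluster-by-time variance estimate that led to the term being dropped. If the interval widens materially, qualify the GTI conclusion accordingly.

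Making a correlated random slope the primary model is not needed: with so few facilities that is a debatable trade-off. As a sensitivity model the random effect is useful. In simulation a model with it had error of 0.04 to 0.09, using a Normal test without small-sample correction.

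The cost is one variance option, one further model on existing data, and a few lines in the SAP. The downsides are a somewhat wider interval and an imprecise SD estimate from at most 12 facilities, fewer after the Cerner exclusions.
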